7.2.2 Dose Adjustments for Specific Nonhematologic Toxicities

7.2.2.1 Infusion Reactions with Obinutuzumab or Rituximab

Manage as in [Section 7.1.1](#). Subjects with Grade 3 infusion reaction upon re-challenge or Grade 4 infusion reactions should not receive further doses of obinutuzumab but can continue acalabrutinib. For rituximab, please refer to the product information for guidance.

7.2.2.2 Progressive Multifocal Leukoencephalopathy or Hepatitis B Reactivation

Permanently discontinue all study drugs.

7.2.3 Dose Adjustments for All Other Nonhematologic Toxicities

[Table 7](#) and [Table 8](#), respectively, display the acalabrutinib and obinutuzumab dose adjustments for all other nonhematologic toxicities (dose reductions are not recommended for rituximab).

[Table 9](#) displays dose modification for toxicity during venetoclax treatment, and [Table 10](#) displays dose adjustments for all other nonhematologic toxicities for which individual study drug attribution is not possible.

Table 7: Acalabrutinib Dose Adjustments for All Other Nonhematologic Toxicities (All Cohorts)

Dose Level	Acalabrutinib Dose
CCI	

Table 8: Obinutuzumab Dose Adjustments for All Other Nonhematologic Toxicities (All Cohorts)

Dose Level	Obinutuzumab Dose
CCI	

7.2.3.1 Cohorts 1 and 2

For \ge Grade 3 nonhematologic toxicity attributable to acalabrutinib, acalabrutinib should be held until toxicity resolves to \le Grade 1, and then restarted at the same dose CCI with the first occurrence; however, for the second occurrence, acalabrutinib should be restarted at CCI. Missed doses should not be made up. Subjects who are stable at a lower dose level for CCI may be dose-escalated by 1 dose level.

For \ge Grade 3 nonhematologic toxicity attributable to obinutuzumab, obinutuzumab should be held until toxicity resolves to \le Grade 1, and then restarted at 1 dose level lower CCI for each occurrence. Missed doses should not be made up. Subjects who are stable at a lower dose level for CCI may be dose-escalated by 1 dose level.

For \ge Grade 3 nonhematologic toxicity for which individual study drug attribution is not possible, subjects should have all drugs held until toxicity resolves to \le Grade 1, and then subjects should be restarted at 1 dose level lower using [Table 10](#). Subjects who are stable at a lower dose level for CCI may be dose-escalated by 1 dose level.

7.2.3.2 Cohorts 3 and 4

After start of CCI for \ge Grade 3 nonhematologic toxicity attributable to study drugs, apply dose medication guidelines to venetoclax first. Per current prescribing information, venetoclax should be held until toxicity resolves to \le Grade 1, and then restarted at the same dose with the first occurrence; however, for the second occurrence, venetoclax should be restarted following

IRB PROTOCOL NUMBER: 2014C0140

OSU PROTOCOL: 14123

the reduction guidelines in [Table 9](#). Missed doses should not be made up. Subjects who are stable at a lower dose for [CCI](#) may be dose-escalated by 1 dose level.

For Grade ≥ 3 nonhematologic toxicity in Cycles 1 and 2 or despite following recommendations for venetoclax, please follow the guidelines noted in [Section 7.2.2](#) for acalabrutinib and/or obinutuzumab.

For \geq Grade 3 nonhematologic toxicity for which individual study drug attribution is not possible, subjects should have all drugs held until toxicity resolves to \leq Grade 1, and then subjects should be restarted at 1 dose level lower again using [Table 10](#). Subjects who are stable at a lower dose level for [CCI](#) may be dose-escalated by 1 dose level.

Table 9: Dose Modification for Toxicity During Venetoclax Treatment (Cohorts 3 and 4)

Dose at Interruption, mg	Restart Dose, mg ^a
CCI	

^a During the [CCI](#) continue the reduced dose for [CCI](#) before increasing the dose.

Table 10: Dose Adjustments for All Other Nonhematologic Toxicities for Which Individual Study Drug Attribution is Not Possible (All Cohorts)

Dose Level	Acalabrutinib Dose	Rituximab Dose	Obinutuzumab Dose	Venetoclax ^a
CCI				

^a During the [CCI](#) continue the reduced dose for [CCI](#) before increasing the dose.

8 Schedule of Activities

Table 11. Schedule of Activities: Cohorts 1 and 2

Tests & Observations (all labs listed here are standard of care except those labeled correlative studies and PK)	Screening	Day 1, 8, 15 of Cycle 1	Day 2 of Cycle 1	Day 1 of Cycles 2-12	Day 1 of Cycles 15, 18, 21, 24 ^H	Relapse/ Disease progression	Safety Follow-up ^I	Discontinua- tion Follow-up ^J	Long-term Follow-up ^K
ACP-196 CCI ¹ PO administration		CCI							
Obinutuzumab administration									
History & physical examination with tumor measurements ¹	X	X		X	X	X	X		
Height	X								
Weight	X	X		X	X	X	X		
ECOG PS	X	X		X	X	X	X		
2 buccal swabs	X								
ECG ²	X								
Concomitant medications	X	X	X	X	X	X	X	X	
Adverse events	X	X	X	X	X	X	X	X	
FISH/stimulated karyotype ³	X					X			
Zap-70 methylation ⁴	X								
IGHV mutational status ⁴	X								
Complete blood count (CBC)	X	X		X	X	X	X		
Chem 10	X	X		X	X		X		
Liver function panel	X	X		X	X		X		
LDH, uric acid	X	X		X	X		X		
Beta-2-microglobulin	X								
Direct antiglobulin test (Coomb's test)	X								

Table 11. Schedule of Activities: Cohorts 1 and 2

Tests & Observations (all labs listed here are standard of care except those labeled correlative studies and PK)	Screening	Day 1, 8, 15 of Cycle 1	Day 2 of Cycle 1	Day 1 of Cycles 2-12	Day 1 of Cycles 15, 18, 21, 24 ^H	Relapse/ Disease progression	Safety Follow-up ^I	Discontinua -tion Follow-up ^J	Long-term Follow-up ^K
Serum or urine HCG ⁵	X								
HBsAg, HBsAb, HCV, anti-HBc	X								
HBV PCR ^{6,7}	X			QM	See footnote 6				
Peripheral blood flow cytometry	X			A	X	X	X		
Serum immunoglobulins	X			A	X		X		
CT scan (chest, neck, abdomen, and pelvis)	X			B	B	X		X	
Bone marrow aspirate and biopsy	X			C	C	X			
Peripheral blood for correlative studies	D	D	D	D	D	D	D		
Peripheral blood for PK ⁸		E							
Bone marrow for correlative studies	X			C	C	X			
Lymph node sample for correlative studies						F			
Quality of life assessment	G	G		G	G	G	G		
Survival status									X

Footnotes are on the next page.

Abbreviations: anti-HBc = hepatitis B core antibody; CCI = clinical performance status; CT = computed tomography; ECG = electrocardiogram; ECOG PS = Eastern Cooperative Oncology

Group performance status; HBsAb = hepatitis B surface antibody; HBsAg = hepatitis B surface antigen; HBV = hepatitis B virus; HCG = human HCG = human chorionic gonadotropin;

LDH = lactate dehydrogenase; PCR = polymerase chain reaction; PK = pharmacokinetics; PO = orally; Q = every; wks = weeks.

Footnotes for Table 11:

1. During the physical examination, palpable lymph nodes will be measured, and data will be collected on a separate case report form.

IRB PROTOCOL NUMBER: 2014C0140

OSU PROTOCOL: 14123

2. ECGs may be obtained at unscheduled time points as clinically indicated.
3. Does not need to be repeated at screening if performed within 60 days of registration
4. Does not need to be repeated if previously performed
5. For women of child-bearing potential only
6. Hepatitis B DNA must be performed in any patient positive for HBsAg or HB core
7. Subjects who are anti-HBc positive should have a quantitative PCR test for HBV DNA performed during screening. Subjects who receive combination therapy with an anti-CD20 monoclonal antibody (i.e., obinutuzumab) should have a quantitative PCR test monthly during treatment and until 12 months after the last dose of anti-CD20 therapy. After that, HBV PCR monitoring should continue quarterly (e.g., every 3 months) until at least 12 months after the last dose of acalabrutinib.
8. As outlined in [Section 13.3](#)
 - A. Cycles 4 and 7 only
 - B. Response evaluations will be done every 12 weeks from randomization for the first 24 months (with the 4th evaluation shifted to Cycle 12 Day 1 rather than Cycle 13 Day 1, to align with study visits), and then every 24 weeks thereafter. Hematology results must be done within 7 days of CT scans. Bone marrow biopsies/aspirates to confirm a CR must be done within 4 weeks of the CT scan, which showed CR.
 - C. PB samples will be used to evaluate for MRD every 3 cycles (at the discretion of the investigator, in line with scheduled response assessments, per protocol).
 - D. Specific times and tube types for correlative samples are outlined in [Section 13.2](#).
 - E. PK analysis will be performed on the first 8 expansion group patients of Cohort 1. Schedule can be found in [Section 13.3](#).
 - F. If performed as part of relapse analysis
 - G. As outlined in [Section 13.4](#)
 - H. Visits to continue every 6 cycles thereafter (\pm 7 days).
 - I. A safety follow-up (SFU) visit is required for all subjects 30 days (+7) from the last dose of study drug.
 - J. After discontinuation of study treatment for any reason, each subject should be followed until disease progression or the start of alternative anticancer therapy. If disease progression has not occurred at the time of the 30-day SFU visit, discontinuation follow-up (DFU) visits should occur approximately every 12 weeks until disease progression. During this period, subjects will be followed via CT scans every 24 weeks; after 2 years in DFU, CT scans will be yearly. AE and concomitant medication reporting, irrespective of seriousness, ends 30 days after the last dose of study drug(s).
 - K. After disease progression or the start of alternative anticancer therapy, all subjects (unless they have withdrawn consent) will be contacted approximately every 12 weeks by telephone, to assess survival until death or lost to follow up.

Table 12: Schedule of Assessments – Cohort 3

Day	Screening	Treatment Phase & Response Evaluation												SFU	Discontinuation follow-up ¹	Relapse/ Disease Progression	Long-term follow-up	
		Cycle 1		Cycle 2			Cycle 3			Cycles 4 -7	Cycles 10, 13, 16, 19, 22	Cycle 24	Cycle 24 q6 cycles					
		1	15	1	8	15	22	1	8	15	22	1	1	1	1			
Study Windows (days)	-28	±3		±3				±3				±3	±3	±3	±7	+7	±7	±7
Study Drug Administration ¹		CCI																
Acalabrutinib																		
Rituximab																		
Venetoclax																		
Procedures																		
History & physical examination with tumor measurements ²	X	X		X				X				X	X	X	X	X	X	
Height	X																	
Weight	X	X	X	X	X	X	X	X	X	X	X	X	X	X	X	X	X	
ECOG PS	X	X	X				X				X	X	X	X	X	X	X	
Disease-related symptoms	X	X	X				X				X	X	X	X	X	X	X	
Vital signs	X	X	X	X	X	X	X	X	X	X	X	X	X	X	X	X	X	
ECG ³	X																	
Concomitant medications	X	X	X	X	X	X	X	X	X	X	X	X	X	X	X	X	X	
Adverse events	X	X	X	X	X	X	X	X	X	X	X	X	X	X	X	X	X	
Pregnancy test ⁴	X																X	
Buccal swabs (2)	X																	
Hepatitis serologies ⁵	X																	
HBV PCR ^{5,6}	X		QM		QM					QM ⁶	See Footnote 6		Q3M					
Direct antiglobulin test (Coomb's test)	X																	
CBC with differential ⁷	X	X	X	X	X	X	X	X	X	X	X	X	X	X	X	X	X	
Chem 10 ⁷	X	X	X	X	X	X	X	X	X	X	X	X	X	X	X	X	X	
Liver Function Panel ⁷	X	X	X	X	X	X	X	X	X	X	X	X	X	X	X	X	X	
LDH, uric acid ⁷	X	X	X	X	X	X	X	X	X	X	X	X	X	X	X	X	X	
Calculated CrCl	X																	

Table 12: Schedule of Assessments – Cohort 3

Day	Screening	Treatment Phase & Response Evaluation												SFU	Discontinuation follow-up ¹	Relapse/ Disease Progression	Long-term follow-up
		Cycle 1		Cycle 2			Cycle 3			Cycles 4 -7	Cycles 10, 13, 16, 19, 22	Cycle 24	Cycle 24 q6 cycles				
		1	15	1	8	15	22	1	8	15	22	1	1	1	1		
Study Windows (days)	-28	±3		±3		±3		±3		±3		±3		±7	+7	±7	±7
Beta-2-microglobulin	X																
Serum immunoglobulins	X									C4, C7	X	X		X			
FISH/stimulated karyotype ⁸	X																X
Zap-70 methylation, IGHV mutational status ⁹	X																
Peripheral blood flow cytometry for B/T/NK cells	X									C4, C7	C16, C19, C22	X	X	X		X	
Peripheral blood for correlative studies	X	C		C			C							C		C	
PK sample collection		D				D			D								
CT scan (chest, neck, abdomen, & pelvis) ¹⁰	X				E					C4, C7	X	X	X; q12 cycles after C36		X ^J	X	
Overall response assessment ¹¹										C4, C7	X	X	X	X	X	X	
Bone marrow biopsy/aspirate ^F	X																X
MRD assessment ^G	X										C10, C16	X			q6 months	X	
Lymph node sample for correlative studies ¹²	X																X
CCI																	
Cell death proteins ^C	X	X		X			X							X		X	
Immunophenotyping ^C	X	X		X			X							X		X	
CCI																	
QoL assessments ¹³	X			X			X				X	C13, C19	X	X			

Table 12: Schedule of Assessments – Cohort 3

		Treatment Phase & Response Evaluation															
Day	Screening	Cycle 1		Cycle 2			Cycle 3			Cycles 4 -7	Cycles 10, 13, 16, 19, 22	Cycle 24	Cycle 24 q6 cycles	SFU	Discontinuation follow-up ¹	Relapse/ Disease Progression	Long-term follow-up
		1	15	1	8	15	22	1	8	15	22	1	1	1	1		
Study Windows (days)	-28	±3		±3				±3		±3		±3	±7	+7	±7		±7
Survival status																	H

Note: All labs listed here are standard-of-care except those labeled correlative studies and PK.

Abbreviations: CCI = cycle; CBC = complete blood count; CrCl = creatinine clearance; CT = computed tomography; ECG = electrocardiogram; ECOG

PS = Eastern Cooperative Oncology Group performance status; HBV = hepatitis B virus; IGHV = immunoglobulin heavy-chain variable; LDH = lactate dehydrogenase; MRD = minimal residual disease; PCR = polymerase chain reaction; PK = pharmacokinetics; PO = orally; Q = every; QoL = quality of life; SFU = safety follow-up; wks = weeks. Additional footnotes are on the next page.

Footnotes to Table 12:

1. Subjects will receive CCI of acalabrutinib CCI before beginning rituximab, starting CCI Venetoclax will commence CCI with standard CCI dosing for CCI prior to full-dose therapy starting CCI. Starting CCI venetoclax should be given first, followed at least 30 minutes later by acalabrutinib. Rituximab should be administered last on days of concomitant dosing.
2. During the physical examination, palpable lymph nodes will be measured, and data will be collected on a separate case report form.
3. Screening laboratory tests and ECG must be done within 14 days prior to initiating treatment. ECGs may be obtained at unscheduled time points as clinically indicated.
4. Serum or urine HCG for women of child-bearing potential only.
5. Hepatitis serologies must include hepatitis B surface antigen (HBsAg), hepatitis B surface antibody (anti-HBs), hepatitis B core antibody (anti-HBc), and hepatitis C (HCV) antibody. In addition, any subjects testing positive for any hepatitis serology must have PCR testing (see exclusion criterion #16).
6. Subjects who are anti-HBc positive should have a quantitative PCR test for HBV DNA performed during screening. Subjects who receive combination therapy with an anti-CD20 monoclonal antibody (i.e., rituximab) should have a quantitative PCR test monthly during treatment and until 12 months after the last dose of anti-CD20 therapy. After that, HBV PCR monitoring should continue quarterly (e.g., every 3 months) until at least 12 months after the last dose of acalabrutinib.
7. Laboratory evaluations must be performed on the date specified, ± 3 days.
8. Does not need to be repeated at Screening if performed within 60 days of registration.
9. Does not need to be repeated if previously performed.
10. CT scans and bone marrow biopsies may be performed within 7 days of the specified dates. Screening CT scans may be used if obtained as standard-of-care within 42 days prior to initiating treatment provided no prior therapy has been given. Screening bone marrow biopsies may, likewise, be used if obtained as standard of care within 90 days prior to initiating treatment provided no prior therapy has been given.

11. Overall response evaluations will be done every 12 weeks from randomization for the first 24 months, and then every 24 weeks. After Cycle 36, CT scan is yearly. Hematology results must be done within 7 days of CT scans. Bone marrow aspirates/biopsies to confirm complete response (CR) must be done within 4 weeks of the CT scan, which showed CR.
12. LN sample should also be sent for correlative studies at time of progressive disease/relapse, if performed as part of disease analysis.
13. EORTC QLQ-C30 will be assessed. See [Appendix 2](#).

A. At investigator decision subjects who are in CR or CR with incomplete bone marrow recovery (CRi) and/or MRD negativity may discontinue acalabrutinib after Cycle 24.

B. **CCI** [REDACTED]

C. Specific times and tube types of correlative samples are outlined in [Section 13.2](#).

D. As outlined in [Section 13.3](#). Drug and metabolite concentrations in plasma will be done by a bioanalytical contract research organization (CRO). **CCI** [REDACTED] Refer to the laboratory manual for instructions on collection and shipment of PK samples.

E. On Day 21, if indicated based on TLS risk.

F. To confirm CR, bone marrow aspirate/biopsy may be performed at any time. At time of bone marrow (BM) biopsy for CR confirmation, bone marrow should also be sent for correlative studies.

G. To confirm CR, draw PB for flow cytometry MRD at any time point if (i) PE/Lab/CT suggestive of CR OR (ii) there is lone residual splenomegaly and/or probable lone reactive lymphadenopathy in absence of other peripheral signs of residual CLL disease. If PB MRD is negative, in 2 to 3 months check BM biopsy/aspirate with BM MRD. If PB MRD is positive, PB MRD may be repeated q3 months until negative and then proceed to BM 3 months after negative PB MRD. Post-CR/CRi, PB MRD is completed every 6 cycles until PD (per [Hallek et al 2008](#)). Site may synchronize this activity with any protocol scheduled PB MRD if the blood draws are ± 2 months apart.

H. After disease progression, subjects will be contacted to assess survival status approximately every 12 weeks until death, withdrawal of consent by subject, lost to follow-up, or study terminated by sponsor, whichever comes first.

I. If disease progression has not occurred at the time of the 30-day SFU, discontinuation follow-up visits should occur approximately every 12 weeks until disease progression. AE and concomitant medication reporting, irrespective of seriousness, ends 30 days after the last dose of study drug(s).

J. CT scans should be performed every 24 weeks. After 2 years in discontinuation follow-up, CT scans will be performed annually.

CCI [REDACTED]

K. **CCI** [REDACTED]

Table 13: Schedule of Assessments – Cohort 4

Day	Screening	Treatment Phase & Response Evaluation												SFU	Discontinuation follow-up ¹	Relapse/ Disease Progression	Long-term follow-up	
		Cycle 1		Cycle 2			Cycle 3			Cycles 4 -7	Cycles 10, 13, 16, 19, 22	Cycle 24	> Cycle 24 q6 cycles					
		1	15	1	2	8	15	1	8	15	22	1	1	1	1	1	1	
Study Windows (days)	-28	±3		±3				±3				±3	±3	±3	±7	+7	±7	±7
Study Drug Administration ¹																		
Acalabrutinib		CCI																
Obinutuzumab																		
Venetoclax																		
Procedures																		
History & physical examination with tumor measurements ²	X	X		X				X				X	X	X	X	X	X	
Height	X																	
Weight	X	X	X	X	X	X	X	X	X	X	X	X	X	X	X	X	X	
ECOG PS	X	X		X				X			X	X	X	X	X	X	X	
Disease-related symptoms	X	X		X				X			X	X	X	X	X	X	X	
Vital signs	X	X	X	X	X	X	X	X	X	X	X	X	X	X	X	X	X	
ECG ³	X																	
Concomitant medications	X	X	X	X	X	X	X	X	X	X	X	X	X	X	X	X	X	
Adverse events	X	X	X	X	X	X	X	X	X	X	X	X	X	X	X	X	X	
Pregnancy test ⁴	X																	X
Buccal swabs (2)	X																	
Hepatitis serologies ⁵	X																	
HBV PCR ^{5,6}	X		QM		QM					QM	See footnote 6	X	Q3M					
Direct antiglobulin test (Coomb's test)	X																	
CBC with differential ⁷	X	X	X	X	X	X	X	X	X	X	X	X	X	X	X	X	X	
Chem 10 ⁷	X	X	X	X	X	X	X	X	X	X	X	X	X	X	X	X	X	
Liver function panel ⁷	X	X	X	X	X	X	X	X	X	X	X	X	X	X	X	X		X
LDH, uric acid ⁷	X	X	X	X	X	X	X	X	X	X	X	X	X	X	X	X		X
Calculated CrCl	X																	

Table 13: Schedule of Assessments – Cohort 4

Day	Screening	Treatment Phase & Response Evaluation												SFU	Discontinuation follow-up ¹	Relapse/ Disease Progression	Long-term follow-up
		Cycle 1		Cycle 2			Cycle 3			Cycles 4 -7	Cycles 10, 13, 16, 19, 22	Cycle 24	> Cycle 24 q6 cycles				
		1	15	1	2	8	15	1	8	15	22	1	1	1	1		
Study Windows (days)	-28	±3		±3			±3			±3	±3	±3	±7	+7	±7		±7
Beta-2-microglobulin	X																
Serum immunoglobulins	X									C4, C7	X	X		X			
FISH/stimulated karyotype ⁸	X															X	
Zap-70 methylation, IGHV mutational status ⁹	X																
Peripheral blood flow cytometry for B/T/NK cells	X									C4, C7	C16, C19, C22	X	X	X		X	
Peripheral blood for correlative studies	X	C		C			C							C		C	
PK sample collection		D				D			D								
CT scan (chest, neck, abdomen, & pelvis) ¹⁰	X				E					C4, C7	X	X	X; q12 cycles after C36		X ^J	X	
Overall response assessment ¹¹										C4, C7	X	X	X	X	X	X	
Bone marrow biopsy/aspirate ^F	X															X	
MRD assessment ^G	X									C10, C16	X			q6 months		X	
Lymph node sample for correlative studies ¹²	X															X	
CCI																	
Cell death proteins ^C	X	X		X			X							X		X	
Immunophenotyping ^C	X	X		X			X							X		X	
CCI																	
QoL assessments ¹³	X			X			X			X	C13, C19	X	X				
Survival status																	H

IRB PROTOCOL NUMBER: 2014C0140**OSU PROTOCOL: 14123**

Note: All labs listed here are standard-of-care except those labeled correlative studies and PK.

Abbreviations: BID = twice daily; C = cycle; CBC = complete blood count; CrCl = creatinine clearance; CT = computed tomography; ECG = electrocardiogram; ECOG PS = Eastern Cooperative Oncology Group performance status; HBV = hepatitis B virus; IGHV = immunoglobulin heavy-chain variable; LDH = lactate dehydrogenase; MRD = minimal residual disease; PCR = polymerase chain reaction; PK = pharmacokinetics; PO = orally; Q = every; QoL = quality of life; SFU = safety follow-up; wks = weeks. Additional footnotes are on the next page.

Footnotes to Table 13:

1. Subjects will receive **CCI** of acalabrutinib **CCI** before beginning obinutuzumab, starting **CCI** Venetoclax will commence **CCI** with standard **CCI** dosing for **CCI** prior to full-dose therapy starting **CCI**. Starting **CCI** venetoclax should be given first, followed at least 30 minutes later by acalabrutinib. Obinutuzumab should be administered last on days of concomitant dosing.
2. During the physical examination, palpable lymph nodes will be measured, and data will be collected on a separate case report form.
3. Screening laboratory tests and ECG must be done within 14 days prior to initiating treatment. ECGs may be obtained at unscheduled time points as clinically indicated.
4. Serum or urine HCG for women of child-bearing potential only.
5. Hepatitis serologies must include hepatitis B surface antigen (HBsAg), hepatitis B surface antibody (anti-HBs), hepatitis B core antibody (anti-HBc), and hepatitis C (HCV) antibody. In addition, any subjects testing positive for any hepatitis serology must have PCR testing (see exclusion criterion #16).
6. Subjects who are anti-HBc positive should have a quantitative PCR test for HBV DNA performed during screening. Subjects who receive combination therapy with an anti-CD20 monoclonal antibody (i.e., obinutuzumab) should have a quantitative PCR test monthly during treatment and until 12 months after the last dose of anti-CD20 therapy. After that, HBV PCR monitoring should continue quarterly (e.g., every 3 months) until at least 12 months after the last dose of acalabrutinib.
7. Laboratory evaluations must be performed on the date specified, \pm 3 days.
8. Does not need to be repeated at Screening if performed within 60 days of registration.
9. Does not need to be repeated if previously performed.
10. CT scans and bone marrow biopsies may be performed within 7 days of the specified dates. Screening CT scans may be used if obtained as standard-of-care within 42 days prior to initiating treatment provided no prior therapy has been given. Screening bone marrow biopsies may, likewise, be used if obtained as standard of care within 90 days prior to initiating treatment provided no prior therapy has been given.
11. Overall response evaluations will be done every 12 weeks from randomization for the first 24 months, and then every 24 weeks. After Cycle 36, CT scan is yearly. Hematology results must be done within 7 days of CT scans. Bone marrow aspirates/biopsies to confirm CR must be done within 4 weeks of the CT scan, which showed CR.
12. LN sample should also be sent for correlative studies at time of progressive disease/relapse, if performed as part of disease analysis.
13. EORTC QLQ-C30 will be assessed. See [Appendix 2](#).

A. At investigator discretion, subjects who are in CR or CRi and/or MRD negativity may discontinue acalabrutinib after Cycle 24.

B. **CCI**

C. Specific times and tube types of correlative samples are outlined in [Section 13.2](#).

D. As outlined in [Section 13.3](#). Drug and metabolite concentrations in plasma will be done by a bioanalytical contract research organization (CRO). **CCI** Refer to the laboratory manual for instructions on collection and shipment of PK samples.

IRB PROTOCOL NUMBER: 2014C0140

OSU PROTOCOL: 14123

- E. On Day 21, if indicated based on TLS risk.
- F. To confirm CR, bone marrow aspirate/biopsy may be performed at any time. At time of bone marrow (BM) biopsy for CR confirmation, bone marrow should also be sent for correlative studies.
- G. To confirm CR, draw PB for flow cytometry MRD at any time point if (i) PE/Lab/CT suggestive of CR OR (ii) there is lone residual splenomegaly and/or probable lone reactive lymphadenopathy in absence of other peripheral signs of residual CLL disease. If PB MRD is negative, in 2 to 3 months check BM biopsy/aspirate with BM MRD. If PB MRD is positive, PB MRD may be repeated q3 months until negative and then proceed to BM 3 months after negative PB MRD. Post-CR/CRi, PB MRD is completed every 6 cycles until PD (per [Hallek et al 2008](#)). Site may synchronize this activity with any protocol scheduled PB MRD if the blood draws are ± 2 months apart.
- H. After disease progression, subjects will be contacted to assess survival status approximately every 12 weeks until death, withdrawal of consent by subject, lost to follow-up, or study terminated by sponsor, whichever comes first.
- I. If disease progression has not occurred at the time of the 30-day SFU, discontinuation follow-up visits should occur approximately every 12 weeks until disease progression. AE and concomitant medication reporting, irrespective of seriousness, ends 30 days after the last dose of study drug(s).
- J. CT scans should be performed every 24 weeks. After 2 years in discontinuation follow-up, CT scans will be performed annually.
- K. **CCI**

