6.4.1.1 Hemorrhage

Serious hemorrhagic events, including fatal events, have occurred in clinical trials with acalabrutinib.

The mechanism for hemorrhage is not well understood. Patients receiving antithrombotic agents may be at increased risk of hemorrhage. Use caution with antithrombotic agents and consider additional monitoring for signs of bleeding when concomitant use is medically necessary. Consider the benefit-risk of withholding acalabrutinib for at least 3 days presurgery and postsurgery. Subjects with hemorrhage should be managed per institutional guidelines with supportive care and diagnostic evaluations as clinically necessary.

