For any Grade ≥ 3 hematologic toxicity, febrile neutropenia, or clinically significant bleeding attributable to study drug, obinutuzumab and acalabrutinib should be held and complete blood count (CBC) monitored weekly. When toxicity resolves to \leq Grade 1 or to baseline, study drugs should be resumed with 1 dose level reduction (obinutuzumab to restart at the next cycle). If subjects are stable at a reduced dose level for [REDACTED] CCI [REDACTED] dose escalation can occur by 1 dose level.

7.2.1.2 Cohorts 3 and 4

During Cycle 1, laboratory parameters will be monitored weekly and will be used in the evaluation of hematologic toxicities. Beginning Cycle 4, laboratory parameters will be monitored on Day 1 of each cycle, while on Cycle 7 results will be monitored Day 1 every 3 cycles. Results will be used in the evaluation of hematologic toxicities.

If subjects experience Grade ≥ 3 hematologic toxicity, febrile neutropenia, or significant bleeding attributable to study treatment within Cycles 1 and 2, acalabrutinib should be held until toxicity resolves to \leq Grade 1 or to baseline. For the first occurrence, acalabrutinib may be restarted at the same dose level [REDACTED] CCI [REDACTED] however, for the second occurrence acalabrutinib should be restarted at [REDACTED] CCI [REDACTED]

After start of venetoclax in [REDACTED] CCI [REDACTED] for any Grade ≥ 3 hematologic toxicity, febrile neutropenia, or clinically significant bleeding attributable to study treatment, recommendations regarding dose interruptions or modifications should be applied to venetoclax first. Recommendations are provided in the current prescribing information for venetoclax (please refer to [Table 9](#) for venetoclax dose reduction guidelines). Consider discontinuing venetoclax for subjects who require dose reductions to less than [REDACTED] CCI [REDACTED] for more than [REDACTED] CCI [REDACTED]

If subjects continue to experience Grade ≥ 3 hematologic toxicity, febrile neutropenia, or significant bleeding, please follow the recommendations for acalabrutinib as noted for **CCI**

G-CSF and GM-CSF may not be used prophylactically but may be used at the treating physician's discretion in subjects with neutropenia related to obinutuzumab, rituximab, venetoclax, or acalabrutinib who are otherwise tolerating therapy and responding well.

Missed doses of either drug should not be made up.

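### For Cohorts 3 and 4, Section 7.2.3.2 gives two different instructions for a Grade 3 or higher nonhematologic event that cannot be tied to one drug, and refers readers to a section with no acalabrutinib hold or reduction step

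*Protocol*

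**What the plan says.** Protocol Section 7.2.3.2 (nonhematologic toxicity, Cohorts 3 and 4) has three paragraphs.

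- **Paragraph 1.** After a start point that is blacked out, Grade 3 or higher toxicity attributed to study drugs (plural, not limited to venetoclax) leads the investigator to "apply dose medication guidelines to venetoclax first". Venetoclax is held until recovery, then "restarted at the same dose with the first occurrence; however, for the second occurrence, venetoclax should be restarted following" the Table 9 reductions.
- **Paragraph 2.** For Grade 3 or higher "toxicity in Cycles 1 and 2 or despite following recommendations for venetoclax, please follow the guidelines noted in" Section 7.2.2, for acalabrutinib and/or obinutuzumab.
- **Paragraph 3.** Where "individual study drug attribution is not possible, subjects should have all drugs held until toxicity resolves to" Grade 1 or lower, the restart is one dose level down, using Table 10. First and later occurrences are not distinguished.

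Section 7.2.2 has two parts. Section 7.2.2.1 covers infusion reactions: obinutuzumab stops in defined cases, acalabrutinib may continue, and rituximab is referred to its product information. Section 7.2.2.2 covers PML and hepatitis B reactivation: "Permanently discontinue all study drugs".

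The acalabrutinib and obinutuzumab dose levels for other nonhematologic toxicity are in Tables 7 and 8 of Section 7.2.3, both labelled for all cohorts. The text on when to hold and how to restart those drugs is in Section 7.2.3.1, which is headed for Cohorts 1 and 2.

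**The concern.** A dose-modification section should give one instruction for each event. Here a regimen-related event with no single culprit meets the triggers of both paragraph 1 and paragraph 3. The two differ on which drugs are held and on whether a first occurrence brings a reduction. A reader sent to Section 7.2.2 for an acalabrutinib step finds none.

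This bears on subject safety and on reporting. Safety is the primary objective of Cohorts 3 and 4 (Section 1.1). No DLTs are defined for them, and Section 10.6 gives dose delays of more than 14 days as its example of a safety concern. SAP Section 6.3 summarises withholding, reduction and relative dose intensity for each drug. SAP Section 13.1 summarises adverse events leading to discontinuation, modification or delay. Which paragraph a treating physician followed can therefore feed into those outputs.

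**Working it through.** The plan states no figure to reproduce. The check sets the passages side by side.

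**Step 1: a first Grade 3 nonhematologic event, after venetoclax has started, attributed to the regimen but not to one drug.**

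| | Paragraph 1 | Paragraph 3 |
|---|---|---|
| Trigger met? | Yes: attributed to study drugs | Yes: no individual attribution |
| Drugs held | Venetoclax first | All drugs then being given |
| First-occurrence restart | Same dose | One level lower |
| Table used | None at first occurrence; Table 9 at second | Table 10 |

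Paragraph 3 cannot be confined to the time before venetoclax, because Table 10 has a venetoclax column. Section 7.2.3.1 avoids the overlap for Cohorts 1 and 2 by sorting events into three groups: acalabrutinib, obinutuzumab, or not attributable. Section 7.2.3.2 has no such sorting. It also does not say how the drug-specific Tables 7 and 8 work alongside the venetoclax-first order.

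**Step 2: the cross-reference.** Section 13.2.2 places sampling before the antibody on Cycle 2 Day 1 and before venetoclax on Cycle 3 Day 1. In SAP Appendix A, Cycle 3 Day 1 is Study Day 57, so Cycles 1 and 2 span 57 − 1 = 56 days. Acalabrutinib is given alone in Cycle 1, and with the antibody from Cycle 2. For a Grade 3 event in this period that is not an infusion reaction, PML or hepatitis B, Section 7.2.2 offers no acalabrutinib hold or reduction step. The same applies to an event that continues despite the venetoclax steps. Paragraph 2 names acalabrutinib and obinutuzumab but not rituximab.

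**Step 3: effect on the summaries.** SAP Section 6.3 counts acalabrutinib as withheld after at least 7 consecutive missed days and as reduced after at least 3 consecutive days at a lower level. For the other drugs, 1 day is enough. For the Step 1 event:

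- Under paragraph 1, if the venetoclax hold suffices, the subject counts as withheld for venetoclax and as reduced for no drug.
- Under paragraph 3, the subject also counts as withheld for acalabrutinib if the hold reaches 7 days, and for the antibody if a dose is missed. The subject counts as reduced for each drug restarted at a lower level for the required time.

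Each cohort has 12 subjects, so one subject changing category moves that drug's percentage by 1/12 = 8.3 points. The documents give no rate for such events, so the number of subjects affected cannot be computed.

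**The case against.** The strongest reply is that this is a drafting slip with a workable reading. Paragraph 3 is the more specific rule and could be taken to override paragraph 1 for non-attributable events. The dose levels are close by, in Tables 7 and 8. Section 7.2.3 does not recommend rituximab dose reductions, Section 7.1.3.3 covers its modification and discontinuation, and Section 7.2.2.1 refers its infusion reactions to the product information. The trial has one site (Section 4.2), and Section 5.3 requires dose delays considered for clinically important events to be discussed with the medical monitor. All of this limits inconsistent handling. It does not remove the fault: the protocol states no precedence, and Tables 7 and 8 visibly offer dose levels without the hold and restart text, which is headed for the other two cohorts.

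A reader might extend the point to Section 7.2.1.2 and to bleeding. There, after venetoclax starts, "recommendations regarding dose interruptions or modifications should be applied to venetoclax first", although Section 6.4.1.1 says "Serious hemorrhagic events, including fatal events, have occurred in clinical trials with acalabrutinib". The documents do not support that extension. Section 7.2.1.2 is sequential: acalabrutinib in Cycles 1 and 2, venetoclax first once it has started, then the acalabrutinib recommendations if events continue. It states its own acalabrutinib rule and never cites Section 7.2.2. Section 6.4.1.1 describes a risk and sets no order for dose changes, so there is nothing for the bleeding rule to contradict.

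A reader might also see a contradiction in Table 10 having a rituximab column when reductions are not recommended for that drug. The cells are blacked out, so this cannot be confirmed.

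**Conclusion.** Section 7.2.3.2 is wrong as written in two respects: paragraphs 1 and 3 give incompatible instructions for one class of event, and paragraph 2 refers to a section that lacks the needed acalabrutinib step. The missing mention of rituximab in paragraph 2 is a smaller gap.

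The effect is confined to Grade 3 or higher nonhematologic events that fall in the overlap or are sent to Section 7.2.2. A reader might infer that all 24 subjects (12 + 12) are affected, but that is the combined cohort size, not a count of affected subjects. Nor do the documents support calling drug-specific tolerability uninterpretable. The primary safety tabulation in Section 14.6.1 is of toxicities by type and grade, dose reductions are only an optional summary there, and SAP Section 6.3 summarises the holds and reductions that actually occurred.

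The conclusion assumes that the blacked-out start point in paragraph 1 is the start of venetoclax, as in the parallel sentence of Section 7.2.1.2. A different start point would shift when the overlap begins, but would remove it only if no paragraph 3 event could occur after it.

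**What to change.** Reconcile the passages in Section 7.2.3.2 so that each event has one instruction:

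1. State which attribution category paragraphs 1 and 3 each cover, or which takes precedence.
2. State how Tables 7 and 8 apply alongside the venetoclax-first order.
3. Replace the reference to Section 7.2.2 with the text and tables intended for Cohorts 3 and 4. If the hold and restart text in Section 7.2.3.1 is meant to apply to these cohorts, say so.
4. Add a reference for rituximab.

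The choice of clinical rule belongs to the sponsor and investigator.

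Rewording cannot change dosing that has already happened, and SAP Section 3.0 describes enrollment of Cohorts 3 and 4 in the past tense. The clinical study report should therefore state, beside the per-drug hold and reduction summaries, which paragraph was applied to each affected event.

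The cost is a protocol wording amendment, a site memo and a short note in the report. No added subjects, visits or tests are needed.
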